CLINICAL STUDY PROTOCOL

A phase II study of brentuximab vedotin in patients with relapsed or refractory EBV- and CD30-positive lymphomas

Indication: EBV and CD30-positive lymphomas
Phase: II

Protocol History

Original; 15-DEC-2013 (version 1.0)

Revised; 3-JUN-2014 (version 1.1)

Investigator & Study Center

[name], PhD, Associate Professor
Seoul National University Hospital
[name]
E-mail: [contact]; [contact]; [contact]

This is an investigator-initiated study. The principal investigator <([name])>, (who may also be referred to as the sponsor-investigator), is the person conducting the study and acting as the sponsor. Therefore, the legal/ethical obligations of the principal investigator include both those of a sponsor and those of an investigator.

PROTOCOL SUMMARY

Study Title: A phase II study of brentuximab vedotin in patients with relapsed or refractory EBV- and CD30-positive lymphomas

Phase: II

Number of Patients: 25

Study Objectives

Primary

- Objective: To evaluate the overall response rate (ORR) of brentuximab vedotin in EBV- and CD30-positive lymphomas

Secondary

- Objective 1: To evaluate the safety profile of brentuximab vedotin using CTCAE version 4.03
- Objective 2: To calculate progression-free survival (PFS) time
- Objective 3: To calculate the duration of response
- Objective 4: To calculate overall survival (OS) time

Exploratory

- Objective 1: To determine the CD30-positive rate of EBV-positive lymphomas
- Objective 2: To compare ORR according to the CD30 expression level
- Objective 3: To compare ORR according to the soluble CD30 level
- Objective 4: To compare ORR according to the EBV copy number

Overview of Study Design:

This is an open-label, non-randomized, multi-center, phase II trial of brentuximab vedotin to evaluate ORR primarily in patients with EBV- and CD30-positive lymphomas. The ORR will be evaluated based on the revised Cheson's criteria¹ or modified SWAT criteria² in case of cutaneous EBV- and CD30-positive lymphomas. Based on the optimal Simon's two-stage design, at least 3 responders among stage 1 patients (N=10) are required to enter into a stage 2. The stage 2 will be delayed until the completion of ≥ 4 cycles of study medication in the last patient in stage 1, so-called interim analysis of stage 1. Although an independent data monitoring committee (IDMC) is unplanned, central study coordinators will monitor the study and safety.

Study Population:

Inclusion criteria

1. Patients with relapsed or refractory EBV- and CD30-positive lymphomas
 - i. EBV-positivity determined by EBV *in situ* hybridization at participating centers
 - a. Extranodal NK/T-cell lymphoma, nasal type

[figure not shown]

b. EBV-positive peripheral T-cell lymphoma, not otherwise specifiedc. EBV-positive diffuse large B-cell lymphoma of the elderlyd. Plasmablastic lymphomae. Lymphomatoid granulomatosisf. Hydroa vacciniform-like T-cell lymphomag. Other EBV-positive lymphoproliferative disorders 
ii. CD30-positivity determined by a specialized hemato-pathologistiii. Relapsed or refractory disease that fails to at least one and maximum four regimens including anthracycline-based chemotherapy; if anthracycline-based regimen is not standard treatment of certain subtypes (e.g. hydroa vacciniforme-like T-cell lymphoma or EBV-positive lymphoproliferative disorder, etc), a prior chemotherapy is acceptable.

2. Age \geq 18 years3. ECOG performance status 0-24. At least one measurable lesion based on revised Cheson's or modified SWAT criteria5. Provision archival tumor tissues (4 μm thickness x 5 unstained slides) and blood samples6. Voluntary written informed consent must be given before performance of any study-related procedure not part of standard medical care, with the understanding that consent may be withdrawn by the patient at any time without prejudice to future medical care.7. Female patient is either post-menopausal for at least 1 year before the screening visit or surgically sterile or if of childbearing potential, agree to practice 2 effective methods of contraception, at the same time, from the time of signing the informed consent through 6 months after the last dose of study drug, or agrees to completely abstain from heterosexual intercourse.8. Male patients, even if surgically sterilized, (i.e., status post vasectomy) agree to practice effective barrier contraception during the entire study period and through 6 months after the last dose of study drug, or agrees to completely abstain from heterosexual intercourse.9. Adequate hematologic function: absolute neutrophil count (ANC) \geq 1,500/μL, platelet count \geq 75,000/μL, and hemoglobin \geq 8.0 g/dL unless there is known hematologic tumor marrow involvement (ANC \geq 1,000/μL and platelet count \geq 50,000/μL if there is known bone marrow involvement)10. Adequate liver function: total bilirubin $<$ 1.5 x the upper limit of the normal (ULN) unless the elevation is known to be due to Gilbert syndrome and ALT or AST $<$ 3 x ULN (AST and AST $<$ 5 x ULN if their elevation can be reasonably ascribed to the presence of hematologic tumor in liver)11. Adequate renal function: serum creatinine $<$ 2.0 mg/dL and/or creatinine clearance or calculated creatinine clearance $>$ 40 mL/minute.12. Expected survival $>$ 3 months

Exclusion criteria

1. Female patient who are both lactating and breast-feeding or have a positive serum pregnancy test
2. Any serious medical or psychiatric illness
3. Known cerebral or meningeal involvement (EBV- and CD30-positive lymphoma or any other etiology), including signs or symptoms of PML
4. Symptomatic neurologic disease compromising normal activities or requiring medication
5. Any sensory or motor peripheral neuropathy greater than or equal to Grade 2
6. Known history of myocardial infarction within 1 year, NYHA class III/IV heart failure, or uncontrolled cardiovascular conditions including cardiac arrhythmias, congestive heart failure (CHF), angina, or electrocardiographic evidence of acute ischemia or active conduction system abnormalities. Recent evidence (within 6 months before first dose of study drug) of a left-ventricular ejection fraction <50%.
7. Any active systemic viral, bacterial, or fungal infection within 2 weeks prior to first study drug dose
8. Any prior chemotherapy and/or other investigational agents within at least 5 half-lives of last dose
9. Prior stem cell transplantation within 100 days or radioimmunotherapy within 8 weeks
10. Prior exposure to CD30-targeted agents
11. Known hypersensitivity to recombinant proteins, murine proteins, or to any excipient contained in the drug formulation of brentuximab vedotin
12. Known human immunodeficiency virus (HIV) positive
13. Known hepatitis B surface antigen-positive, or known or suspected active hepatitis C infection
14. Another malignancy within 3 years before the first dose or previously diagnosed with another malignancy and have evidence of residual disease. Patients with nonmelanoma skin cancer or carcinoma in situ of any type are not excluded if they have undergone complete resection.

Duration of Study: This study will last approximately 30 months to reach the final analyses of the ORR and PFS (24 months of enrollment plus 6 months of additional follow-up after the last patient-in).

STUDY OVERVIEW DIAGRAM

SCHEDULE OF EVENTS

Timetables: screening ~ end of treatment

	Screening	Cycle 1	Cycle 2	Cycles 3~15	Cycle 16	EOT/EOS	FU ^a
	-28 to D1	D1	D1	D1	D1	30 ± 7 after last IP dose	q 3 mo till study closure
Visit window, days		± 3	± 3	± 3	± 3		
Informed consent	X						
Inclusion/exclusion	X						
Demographics	X						
Medical history	X						
Tumor specimen and biomarker sample	X ^b						
Height	X						
Weight	X	X	X	X	X		
Physical exam	X	X ^c	X	X	X	X	X
Serum β-hCG	X ^d						
Urine pregnancy test		X					
Vital signs	X	X ^e	X	X	X	X	X
ECOG performance status	X		X	X	X		
B symptoms	X	X	X	X	X	X	X
Hematology and chemistry ^f	X	X	X	X	X	X	X
12-lead ECG	X						
Concomitant medication	Concomitant medications and procedures will be recorded from signing the main ICF through 30 days after the last dose of brentuximab vedotin.						
AE reporting		Recorded from first dose of study drugs through 30 days after the last dose of brentuximab vedotin.					
SAEs	SAEs will be collected from signing of the main ICF through 30 days after the last dose of brentuximab vedotin.						
CTs of the neck, abdomen, and pelvis ^g	X		X	X		X	
Skin evaluation ^h	X		X	X		X	
PET/CT ⁱ	X		X				
Survival and disease status							X ^j

- a. All treated patients will be followed for PFS and OS status every 12 weeks (\pm 1 week) until the study closure. For patients who have progressive disease, survival/disease status and information regarding the initiation of an alternative lymphoma treatment may be obtained by phone call.
- b. Tumor tissue at any time will be collected (five unstained slides at 4 μ m thickness or a paraffin-embedded block) after the patient has signed the screening ICF. This will be used to assess CD30 status using Ber-H2 antibody (DAKO, Glostrup, Denmark) and biomarkers associated with sensitivity or resistance to brentuximab vedotin (eg, beta3- tubulin etc). Biomarker samples will be collected (EDTA 5mL x1 plus SST 3mL x1) to assess lymphocyte subsets and soluble CD30 quantification.
- c. The Cycle 1 Day 1 physical exam is not required if the screening physical examination was conducted within 7 days before administration of the first dose of brentuximab vedotin. A limited physical exam may be administered at the treating physician's discretion.
- d. A serum β -hCG pregnancy test will be performed for women of childbearing potential during screening. A negative urine pregnancy test is required if the serum pregnancy test was not done within 7 days of the first dose of study drug.
- e. Vital signs should be measured at screening and within 1 hour prior to infusion of brentuximab at day 1 of each cycle and EOT.
- f. A blood sample for hematology and serum chemistry including LDH will be obtained at screening and pre-dose at day 1 of each cycle and EOT. Hematology and chemistry blood samples for cycle 1, day 1 may be collected within 7 days prior to dosing to ensure patient eligibility on study day 1.
- g. Response to treatment and disease status assessments will be evaluated according to the Revised Response Criteria for Malignant Lymphomas¹ and the modified SWAT criteria.² MRI scans may be substituted for CT scans only if a patient 1) has a glomerular filtration rate of less than 60 mL/min such that IV contrast presents a risk of renal failure, 2) develops anaphylaxis to IV contrast, or 3) becomes pregnant during long-term follow-up. If use of MRI is required, a consistent scanning modality must be maintained.

During the treatment phase CT scans will be performed at:

- 1) Screening
- 2) CT scans of involved sites after cycle 2 of brentuximab every 6 weeks (window, \pm 7 days) until progressive disease or 16th cycle of brentuximab vedotin. After last dose of cycle 16: between 4 and 8 weeks following last dose of brentuximab. During the follow-up period: every 3 months until the study closure.
- h. In case of cutaneous lymphomas, total body skin scoring is calculated based on modified Severity Weighted Assessment Tool (mSWAT). This involves the direct assessment of the BSA of each type of skin lesions (palm plus fingers of the patient = approximately 1% BSA) in each of 12 areas of the body, multiplying the sum of the BSA of each lesion by a weighting factor (patch=1, plaque =2, and tumor = 3 or 4) and generating a sum of the subtotals of each lesions.
- i. This is mandatory at sites where a PET scanner is available. For all patients, if the screening FDG-PET scan is non-avid, the second interim FDG-PET scan will not be performed.
- j. Subjects will be followed for survival disease status every 3 months till the study closure.

TABLE OF CONTENTS

STUDY OVERVIEW DIAGRAM	5
SCHEDULE OF EVENTS	6
LIST OF TABLES	9
1 BACKGROUND AND STUDY RATIONALE.....	16
1.1 Scientific Background	16
1.1.1 Disease Under Treatment.....	16
1.1.2 Study Drug	16
1.2 Preclinical Experience.....	17
1.3 Pharmacology and Drug Metabolism in Humans	17
Pharmacokinetic properties	17
1.4 Clinical Experience	18
1.5 Study Rationale and Selection of Study Drug Doses.....	21
1.6 Potential Risks of brentuximab vedotin	22
2 STUDY OBJECTIVES	25
2.1 Primary Objectives.....	25
2.2 Secondary Objectives.....	25
2.3 Exploratory Objectives.....	25
3 STUDY ENDPOINTS	26
3.1 Primary Endpoints.....	26
3.2 Secondary Endpoints.....	26
3.3 Exploratory Endpoints	26
4 STUDY DESIGN.....	27
4.1 Overview of Study Design.....	27
4.2 Number of Patients.....	27
4.3 Duration of Study.....	27
5 STUDY POPULATION	28
5.1 Inclusion Criteria.....	28
5.2 Exclusion Criteria.....	29
6 STUDY DRUG	30
6.1 Brentuximab Vedotin Administration.....	30
6.2 Dose Modification Guidelines	31
6.3 Excluded Concomitant Medications and Procedures.....	32
6.4 Permitted Concomitant Medications and Procedures	33
6.5 Precautions and Restrictions	33
6.6 Management of Clinical Events	34
6.7 Description of Investigational Agents.....	37
6.8 Preparation, Reconstitution and Dispensing	38
6.9 Packaging and Labeling	38
6.10 Storage, Handling and Accountability	38

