4 STUDY DESIGN

4.1 Overview of Study Design

This is an open-label, non-randomized, multi-center, phase II trial of brentuximab vedotin to evaluate ORR primarily in patients with EBV- and CD30-positive lymphomas. The ORR will be evaluated based on the revised Cheson's criteria¹ or modified SWAT criteria² in case of cutaneous EBV- and CD30-positive lymphomas. Patients may receive up to 16 cycles of brentuximab vedotin.

Tumor measurements will be assessed (CT and PET scans) at screening, after completion of cycle 2 (Cycle 2 Day 21 ± 7 day), and at 4 to 8 weeks after the last dose of brentuximab vedotin. CT scans only will be used for the disease assessment follow-up every 3 months until the study closure.

Safety will be evaluated according to National Cancer Institute Common Terminology Criteria for Adverse Events (NCI CTCAE), Version 4.03, as well as by measuring changes from baseline in the patient's vital signs, ECOG performance status, electrocardiogram (ECG), and clinical laboratory results.

Patients may discontinue therapy at any time. Patients will attend the EOT visit 30 (± 7) days after completion of their last dose of brentuximab vedotin.

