12.3 Revised response criteria for malignant lymphoma

Complete Remission (CR)

1. Complete disappearance of all detectable clinical evidence of disease and disease-related symptom if present prior to therapy.
2. The spleen and/or liver, if considered enlarged prior to therapy on the basis of a physical examination or CT scan, should not be palpable on physical examination and should be considered normal size by imaging studies, and nodules related to lymphoma should disappear.
3. If the bone marrow was involved by lymphoma prior to treatment, the infiltrate must have been cleared on repeat bone marrow biopsy and EBV should be negative by EBV in situ hybridization (ISH).
4. In patients for whom FDG by PET is avid, incorporation of interim PET imaging results as follows: All CR requirements as described above. However, if a patient's PET scan was positive before therapy, a post-treatment residual mass of any size is permitted as long as it is PET negative

Partial Remission (PR)

1. $\geq 50\%$ decrease in sum of the product of the diameters (SPD) of up to 6 of the largest dominant nodes or nodal masses.
2. No increase in the size of the other nodes, liver, or spleen.
3. Splenic and hepatic nodules must regress by $\geq 50\%$ in their SPD or, for single nodules, in the greatest transverse diameter.
4. With the exception of splenic and hepatic nodules, involvement of other organs is usually assessable and no measurable disease should be present.
5. Bone marrow assessment is irrelevant for determination of a PR if the sample was positive prior to treatment. However, if positive, the EBV-positivity should be specified by EBV ISH. Patients who achieve a CR by the above criteria, but who have persistent morphologic or molecular bone marrow involvement will be considered partial responders.
6. No new sites of disease should be observed (e.g., nodes > 1.5 cm in any axis).
7. For patients with FDG-avidity, an interim assessment should be made. For patients whose PET scan was positive before therapy, the post-treatment PET scan should be positive in at

least one previously involved site.

Stable Disease (SD)

1. Failure to attain the criteria needed for a CR or PR, but not fulfilling those for progressive disease
2. PET imaging should be positive at prior sites of disease with no new areas of involvement on the post-treatment PET scan.

Relapsed Disease (RD; after CR) or Progressive Disease (PD; for Patients with PR or SD)

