1. Appearance of any new lesion more than 1.5 cm in any axis during or at the end of therapy, even if other lesions are decreasing in size.
2. At least a 50% increase from nadir in the SPD of any previously involved nodes, or in a single involved node, or the size of other lesions (e.g., splenic or hepatic nodules). To be considered progressive disease, a lymph node with a diameter of the short axis of less than 1.0 cm must increase by $\geq 50\%$ and to a size of 1.5×1.5 cm or more than 1.5 cm in the long axis.
3. At least a 50% increase in the longest diameter of any single previously identified node more than 1 cm in its short axis.
4. If FDG-PET imaging has been obtained, PD should only be designated if the CT criteria for progression have been met and the lesions are PET positive for patients with PET-positive disease prior to therapy. FDG-PET is not mandatory for surveillance of progression.

Response	Definition	Nodal masses	Spleen, liver	Bone marrow
CR	Disappearance of all evidence of disease	(a) FDG-avid or PET positive prior to therapy; mass of any size permitted if PET negative (b) Variably FDG-avid or PET negative; regression to normal size on CT	Not palpable, nodules disappeared	Infiltrate cleared on repeat biopsy; if indeterminate by morphology, IHC should be negative
PR	Regression of measurable disease and no new sites	≥ 50% decrease in SPD of up to 6 largest dominant masses; no increase in size of other nodes (a) FDG-avid or PET positive prior to therapy; one or more PET positive at previously involved site (b) Variably FDG-avid or PET negative; regression on CT	≥ 50% decrease in SPD of nodules (for single nodule in greatest transverse diameter); no increase in size of liver or spleen	Irrelevant if positive prior to therapy; cell type should be specified
SD	Failure to attain CR/PR or PD	(a) FDG-avid or PET positive prior to therapy; PET positive at prior sites of disease and no new sites on CT or PET (b) Variably FDG-avid or PET negative; no change in size of previous lesions on CT		
RD or PD	Any new lesion or increase by ≥ 50% of previously involved sites from nadir	Appearance of a new lesion(s) > 1.5 cm in any axis, ≥ 50% increase in SPD of more than one node, or ≥ 50% increase in longest diameter of a previously identified node > 1 cm in short axis Lesions PET positive if FDG-avid lymphoma or PET positive prior to therapy	> 50% increase from nadir in the SPD of any previous lesions	New or recurrent involvement

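### The scheduled CT field leaves out the chest and narrows to involved sites on treatment, so chest disease not found at screening and new lesions elsewhere can escape the CR, PR and PD calls

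*Combined protocol and SAP*

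**What the plan says.** The CT row of the Schedule of Events reads "CTs of the neck, abdomen, and pelvis". It is marked at screening, cycle 2, cycles 3 to 15 and EOT/EOS; its follow-up cell is blank. Footnote g, attached to that row, gives the on-treatment extent and timing as "CT scans of involved sites after cycle 2 of brentuximab every 6 weeks", followed by a scan 4 to 8 weeks after the last dose of cycle 16 and then scans every 3 months, without naming regions for these later scans.

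The PET/CT row is marked at screening and cycle 2 only. Footnote i says "This is mandatory at sites where a PET scanner is available" and adds that "if the screening FDG-PET scan is non-avid, the second interim FDG-PET scan will not be performed". Section 4.1 states "Tumor measurements will be assessed (CT and PET scans) at screening, after completion of cycle 2" and again 4 to 8 weeks after the last dose. It then says "CT scans only will be used for the disease assessment follow-up every 3 months until the study closure". It names no body regions.

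Appendix 12.3 defines response without restriction by site. CR requires "Complete disappearance of all detectable clinical evidence of disease". PR requires that no new site of disease is seen. PD includes "Appearance of any new lesion more than 1.5 cm in any axis during or at the end of therapy", even when other lesions are shrinking.

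**The concern.** The primary endpoint rests on statements about the whole patient: all disease gone, or no new disease. The scheduled CT looks at part of the patient, and on treatment at a smaller part still. A scan of involved sites cannot show that there are no new sites.

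At stake are ORR, the CR rate (a secondary endpoint in section 3.2), PFS and duration of response. This is a single-arm trial, so there is no comparator in which a detection error could cancel, and the protocol describes no central imaging review. Some sites will add the chest by habit or have PET, and others will not, so detection would also vary by centre. The decision rules in section 7.1.1 are sensitive to single patients: one false responder turns 2/10 into continuation, or 7/22 into rejection of the null.

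**Working it through.** **Step 1. Which scans cover which regions.**

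- Screening: CT of neck, abdomen and pelvis (CT row). PET/CT where a scanner exists. Without PET, no scheduled scan looks at the chest.
- After cycle 2: CT of involved sites (footnote g) or of neck, abdomen and pelvis (CT row); the two disagree. PET/CT where available, and only if the baseline scan was avid.
- After that, every 6 weeks to progression or cycle 16: the same CT conflict, and no PET.
- 4 to 8 weeks after the last dose: CT with no regions stated in footnote g. Section 4.1 adds PET, but the PET/CT row has no mark at EOT/EOS.
- Follow-up: CT only, every 3 months, according to footnote g and section 4.1, with no regions stated. The CT row's follow-up cell is blank.

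PET does not settle the matter even where it is done. Its body coverage is not stated, and Appendix 12.3 allows PD to be designated only if the CT criteria for progression are also met.

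**Step 2. What can be missed, and which endpoint it moves.**

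- Chest disease known at baseline: it counts as an involved site and is followed. No gap.
- Chest disease not detected at screening that persists but regresses: a true PR can be called CR. The CR rate rises; ORR does not change.
- Disease that is new or growing in an unscanned region while the visible disease meets CR or PR: a true non-responder is called a responder. ORR rises.
- A new lesion outside the scanned field in a patient already counted as a responder or as stable: PD is recorded late. PFS lengthens and, in responders, so does duration of response.
- Unscanned chest nodes that shrink: PR is judged on up to six of the largest dominant nodes or masses, so leaving out shrinking ones can turn a true PR into SD. ORR falls.

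Four of these five cases involve a gap. Three of those four push results upward and one pushes ORR downward.

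**Step 3. The plan's own design.** Inputs from section 7.1.1: P0 = 0.20, P1 = 0.45, continue with at least 3 of 10, reject with at least 8 of 22. With X1 ~ Bin(10, p) and X2 ~ Bin(12, p),

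P(reject) = sum over x = 3 to 10 of P(X1 = x) × P(X2 ≥ 8 − x).

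At p = 0.20 the terms for x = 3 to 8 are 0.01461 + 0.01809 + 0.01167 + 0.00399 + 0.00073 + 0.00007, and those for x = 9 and 10 are negligible. The total is 0.049. At p = 0.45 the result is 0.806. The stated design reproduces, and 22/(1 − 0.10) = 24.4, which rounds up to 25. Changing the CT field alters none of this.

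**Step 4. Illustration of sensitivity.** Suppose a share m of true non-responders is called CR or PR because of unseen disease. The documents give no value for m; the range below is assumed. The observed null rate is 0.20 + 0.80m.

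- m = 0: rate 0.200, type I error 0.049
- m = 1%: rate 0.208, type I error 0.060
- m = 2.5%: rate 0.220, type I error 0.079
- m = 5%: rate 0.240, type I error 0.120

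**The case against.** The strongest reply is that the gap is narrower than the CT row suggests. Much of that reply stands.

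- A reader might infer that intrathoracic disease has no scheduled measurement at all, for instance in lymphomatoid granulomatosis with lung lesions. The documents do not support this: once such disease is known, footnote g schedules it as an involved site every 6 weeks.
- A reader might infer that PET never helps. It is mandatory wherever a scanner exists, section 4.1 has a PET after the last dose, and the documents do not say that any site lacks a scanner. PET therefore reduces the problem, but only conditionally, and by the Schedule not after cycle 2.
- A reader might infer that the error can only favour the drug. The case of shrinking chest nodes in step 2 shows otherwise.
- A reader might take 0.120 as the trial's false-positive rate. It is the top of an assumed range. ORR is inflated only when visible disease meets CR or PR, unseen disease is new or growing, and PET does not show it. No figure in the documents sizes that joint event.

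Involved-site CT may also have been chosen deliberately, and the missing chest may be a drafting slip. Neither possibility removes the problem. The row and its footnote contradict each other, nothing corrects the omission, and the response criteria ask for more than either field can show.

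**Conclusion.** The point holds in limited form and should be fixed. As written, the plan can miss chest disease not detected at screening, chiefly at sites without PET, and new lesions outside involved sites, especially after cycle 2. This can inflate the CR rate, inflate ORR when the unseen disease is new or growing, and delay PD and so lengthen PFS and duration of response. The direction is mainly, not wholly, upward.

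The size cannot be computed, because the documents give neither a rate of chest involvement nor the number of sites without PET. The step 4 figures show only that the rule has little slack: its exact error is already 0.049 against a nominal 0.05, so even a 1% miscall rate would take it over. The Simon design itself is correct and is not in question.

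**What to change.** 1. Change the CT row to *CT of the neck, chest, abdomen and pelvis*.
2. Reconcile footnote g with the row, so that every assessment used for CR, PR or PD uses that same field plus any other site involved at baseline.
3. Reconcile the Schedule with section 4.1 on PET 4 to 8 weeks after the last dose (in 4.1, not marked in the PET/CT row) and on the 3-monthly follow-up CT (in footnote g and 4.1, blank in the CT row).

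These are wording changes, and the scans fall in sessions already scheduled. The cost is extra radiation and reading time per scan. It is not confined to the added chest: if involved-site CT is what is now intended, the fixed field widens each on-treatment scan, about 8 over a full course (16 cycles × 3 weeks = 48 weeks; 48/6 = 8), and the follow-up scans used to date PD. The change should be made before enrolment, because a region that was not scanned cannot be assessed afterwards.
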